# 3.0 Background\*

3.1 *Current MDACC practice protocols* 

As a major tertiary cancer center, MD Anderson Cancer Center has a significant population of patients who present for staging of known breast

cancer (BC) which was already diagnosed at an outside facility (OSF), or who have OSF imaging findings that are assigned category 5 (highly suspicious with the probability of malignancy >95%) or 4C (suspicious with the probability of malignancy 50-95%) according to the American College of Radiology (ACR) Breast Imaging Reporting and Database System (BI-RADS) on OSF imaging [1]. Precise delineation of the extent of disease in the affected breast and evaluation of the contralateral breast are crucial for surgical treatment planning in BC patients [2]. Even in patients with no known BC, a second opinion at a specialized cancer center can make a significant impact on clinical management, changing the original interpretation in 36-47% of lesions [3, 4]. In patients who present with known BC at MDACC, the rate of upstaging upon second opinion interpretation and possible re-imaging is 25%, which changes surgical management in 12% of patients [5]. At the same time, the reoperation rate after breast conservation surgery in BC patients is 19% [5]. This is suboptimal and may be due to underestimation of tumor size, but this rate is lower than the national rate, which reaches 30% [2].

The current protocol for staging of OSF BC cases consists of a second read of interpretable OSF mammograms or repeating technically suboptimal mammograms, followed by ultrasound, ultrasound-guided and/or stereotactic-guided biopsies, when indicated. Some patients also require breast MRI with second look ultrasound and ultrasound- or MRIguided biopsies, which prolongs work-up and delays treatment.

At our institution, using ultrasound and MRI almost doubles the number of additional suspicious breast lesions found on mammography. 45% of these additional lesions are malignant. The sensitivities of mammography (MG), US, and MRI are 36, 71, and 85%, respectively, and their specificities are respectively 76, 68, and 39%, making MRI the most sensitive, and the MG the most specific modality. 18% of additional malignant lesions at MDA are found on MRI only [6]. Unfortunately, the need for breast MRI often delays treatment due to the limited availability of magnet time. MRI is also an expensive imaging test, further limiting access.

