## 5.8 Multiple reader study design

Low-energy images produced as a part of CEM are of sufficient quality for clinical interpretation (equivalent to directly acquired 2D mammographic images), and will be interpreted accordingly by radiologists.

The reader study will have 2 components:

1. The first interpretation of the entire CEM study, including all its components, will be done clinically by one radiologist after the exam is performed. Its results will be actionable and will affect the patient's management.

2. Multiple reader study. The results of this study will not be used for clinical care, and will not be reported to the patients or referring clinicians.

Each patient's study will contain LE images (FFDM equivalent), DBT images, and CEM subtraction images. All these components will be separated and presented to radiologists in different combinations for within-subject comparison. As a part of the multi-reader component, the study images for every patient will be reviewed in 4 sets by 5 radiologists each. Images for the same patients will be read by radiologists with an interval of at least 2 month to prevent case memorization.

1. LE (FFDM equivalent) images only

2. LE (FFDM equivalent) with DBT

3. LE followed by DBT followed by CEM subtraction images

4. LE followed by subtraction images (complete CEM study)

The study radiologists will be aware of the patients' inclusion criteria, but will be blinded to the clinical diagnostic reports, any and all comparison images of any modality outside of the assigned protocol, and the pathology report.

5.9 The sequence of the imaging studies and the parameters to be collected are presented below. The reporting will be done using ACR BI-RADS Fifth edition recommendations.

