# 12.0 Withdrawal of Subjects\*

*12.1* The patients may refuse participation at any time for any reason.

12.2 The subjects will be withdrawn from the research without their consent in the following situations:

- The patient has consented to the study but is determined to be ineligible before CEM is completed
- The patient does not complete CEM imaging
- The patient refuses a biopsy or chooses to have a biopsy at an outside *institution*
- In these cases, the patients' research files will be removed and any collected data will not be used for analysis.

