### 15.2 Sample size

In two recent studies, the authors reported the accuracies of 78.0% (versus 69.0% for MG) [35] and 79.8% (versus 65.3% for MG) [36], respectively. We utilize these clinical evidences for our sample size justifications. Using a two-sided extended McNemar test with a significance level of 0.05, a sample size of 83 patients provides 80% power to detect an accuracy difference of 12% between the two modalities of CEM and FFDM assuming the discordant of 20%. The method proposed by Wu (2018) was used to calculate the sample size, where the multiple lesions were adjusted via the average number of lesions and the variance that were assumed to be 1.4 and 1, respectively [37]. We further assumed the intracluster correlation of 0.4, and 0.2 for the intracluster correlation of the discordant pairs.

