## **19.0 Resources Available**

19.1 A full-field digital mammography system capable of providing lowand high-energy exposures to the breast under the same compression, as well as producing subtracted contrast images, such as Senographe Pristina (GE Healthcare, Buc, FR)

19.2 A CEM- guided biopsy device (GE Healthcare, Buc, FR) is planned to be installed in November 2020

*19.3 %FTE is requested for a dedicated clinical mammography technologist and a clinical study coordinator* 

19.4 Approximately 5-8 patients per day are seen in the multidisciplinary clinic for staging of BC diagnosed at OSF. This results in a minimum of 1,305 potentially eligible patients. Recruiting 6% of the eligible pool, or 2 patients per week will allow completion of recruitment within 12 months.

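### Does the single, unsourced 20% discordance behind the 83-patient sample size (Section 15.2) call for a change to the plan?

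*Combined protocol and SAP*

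**What the plan says.** Section 15.2 takes its effect size from two published comparisons with mammography: "the authors reported the accuracies of 78.0% (versus 69.0% for MG) [35] and 79.8% (versus 65.3% for MG) [36], respectively". The test is given as "Using a two-sided extended McNemar test with a significance level of 0.05", and 83 patients are said to provide 80% power "to detect an accuracy difference of 12% between the two modalities of CEM and FFDM assuming the discordant of 20" per cent. Lesions per patient are assumed to have mean 1.4 and variance 1, and the clustering inputs are: "We further assumed the intracluster correlation of 0.4, and 0.2 for the intracluster correlation of the discordant pairs". The calculation follows a cited method for clustered McNemar data.

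The Study Summary (1.0) and Section 10.1 repeat 83 as the sample size and the number of subjects. Section 12.2 withdraws patients who do not complete CEM, refuse biopsy or have it elsewhere, and says that their "research files will be removed and any collected data will not be used for analysis". On feasibility, Section 19.4 says: "Recruiting 6% of the eligible pool, or 2 patients per week will allow completion of recruitment within 12 months".

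**The concern.** In a paired comparison of accuracy, the sample size depends on two quantities: the difference, and the proportion of lesions on which the two reads disagree about being right. The cited studies support the difference (gaps of 9.0 and 14.5 points, mean 11.75). They are quoted for marginal accuracies only, so they cannot fix the disagreement. Section 15.2 simply assumes 20%.

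If the true discordance were higher and the difference still 12 points, power would be below 80%, and the section gives no idea how far below. Two further gaps point the same way. The text does not say how each of the two intracluster correlations enters the formula. And 83 serves both as the number in the power calculation and as the number of subjects, although Section 12.2 removes some patients from analysis and no replacement is mentioned. At stake is whether a non-significant primary result would come from a study with 80% power or one with much less.

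**Working it through.** **Inputs (Section 15.2).** Two-sided alpha 0.05; difference d = 0.12; discordance p = 0.20; 83 patients; lesions per patient with mean 1.4 and variance 1; intracluster correlations 0.4 and 0.2. The cited clustered formula is not printed in the documents, so I used the McNemar normal approximation with a design effect (DE).

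**Step 1: reproduce the stated figure.** Independent lesions needed for 80% power:

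(1.96·√0.20 + 0.8416·√(0.20 − 0.12²))² / 0.12² = 106.6.

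Patients = 106.6 × DE / 1.4.

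- Mean cluster size with correlation 0.2: DE = 1 + (1.4 − 1) × 0.2 = 1.08, giving 82.3, so 83 patients.
- Variance-weighted cluster size with the product of the correlations: DE = 1 + ((1.4² + 1)/1.4 − 1) × 0.4 × 0.2 = 1.089, giving 82.9, so 83 patients.

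Power = Φ((d√L − 1.96√p)/√(p − d²)), with L = 83 × 1.4 / DE. This is 80.4% (L = 107.6) and 80.0% (L = 106.7). The plan's figure is reproduced. Not every reading reproduces it: the variance-weighted form gives 75.2% with correlation 0.2 alone and 67.8% with 0.4 alone.

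**Step 2: vary the discordance, holding 83 patients and 12 points.**

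| Discordance | Power, DE 1.08 | Power, DE 1.089 |
|---|---|---|
| 15% | 90.6% | 90.4% |
| 20% | 80.4% | 80.0% |
| 25% | 70.7% | 70.4% |
| 30% | 62.6% | 62.2% |
| 35% | 55.8% | 55.5% |
| 40% | 50.3% | 50.0% |

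The choice between the two readings moves power by less than half a point.

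**Step 3: how plausible are these values?** For accuracies a and b, discordance cannot be below a − b, and it equals a(1 − b) + b(1 − a) when the reads are independent.

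- 78.0/69.0: minimum 9%; independent 0.78 × 0.31 + 0.69 × 0.22 = 39.4%.
- 79.8/65.3: minimum 14.5%; independent 0.798 × 0.347 + 0.653 × 0.202 = 40.9%.

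The correlation between reads implied by p is (independent value − p) / (2√(a(1 − a)b(1 − b))).

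- At 20%: 0.51 and 0.55.
- At 35%: 0.11 and 0.15.
- At 40%: −0.02 and 0.02.

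Section 5.8 defines the fourth reading set as "LE followed by subtraction images (complete CEM study"), so the CEM read contains the comparator's images, and both reads are judged against the same pathology. A clearly positive correlation is expected. About 0.5 is reasonable and about zero is not.

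**Step 4: enrolled or analysed.** The documents give no loss rate; 5% and 10% are assumptions. If 83 are enrolled and discordance is 20%:

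- 5% loss: 83 × 0.95 = 78.9 analysed, power 78%.
- 10% loss: 83 × 0.90 = 74.7 analysed, power 76%.

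The recruitment text does not settle the meaning of 83: 6% of 1,305 is 78, and 2 per week for 52 weeks is 104.

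**The case for a change.** The best case for acting is that power depends heavily on one assumed number, that the sponsor offers no argument for it, and that a paragraph and a short table would cost almost nothing. The cited accuracies allow discordance well above 20%. The institution's own figures for additional lesions, in Section 3.1, describe a weaker comparator than the cited studies do: "The sensitivities of mammography (MG), US, and MRI are 36, 71, and 85%, respectively, and their specificities are respectively 76, 68, and 39" per cent. With 45% of such lesions malignant, mammographic accuracy is 0.45 × 0.36 + 0.55 × 0.76 = 58%, against 65% to 69% in the cited studies.

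It stands that the 20% is unsourced, that the handling of the two correlations is left to the cited method, and that 83 is not defined. The step from there to a power problem does not stand. The uncertainty runs both ways: 15% discordance also fits the cited accuracies and gives about 90% power. The Section 3.1 figures do not imply lower power either, because a CEM read with much better sensitivity and no worse specificity would raise the difference as well as the discordance. Nor would a reader of a null result be left guessing. Section 15.3 plans 95% confidence intervals for accuracy, and the paired data will give the observed discordance.

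**Conclusion.** No change to the plan follows. The 83 patients and 80% power are correct for the stated inputs under two readings of the clustering terms. The 20% discordance implies a correlation between reads of about 0.5, which suits a design in which one read contains the other's images. The sensitivity is real: about 10 points of power are gained at 15% and lost at 25%, and about 18 are lost at 30%. The 50% figure needs nearly independent reads. These results rest on a fixed 12-point difference and on the normal approximation used in place of the cited formula.

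Writing down the formula, a rationale for 20%, a two-sided table or the meaning of 83 would be optional clarification and would alter no result. Enrolling extra patients to cover withdrawals would rest on a loss rate that the documents do not give, to recover about 2 to 4 points of power at an assumed 5% to 10% loss.

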### 15.3 Statistical analysis plan

Descriptive statistics will be used to summarize clinical variables of interest. Specifically, categorical measures will be summarized using frequencies and percentages and continuous measures will be summarized using means, standard deviations, medians, and ranges. Outcome variables of cancer detection rate, accuracy, sensitivity, specificity, PPV, and NPV will be estimated along with 95% confidence intervals; and compared between the modalities using the McNemar test or the weighted generalized score statistic proposed by Kosinski [38], if deemed appropriate . To account for multiple lesions, outcome variables will be analyzed using generalized liner mix models or extended McNemar's test [39-41], and additional analyses may be further performed if deemed appropriate.

# 16.0 Provisions to Protect the Privacy Interests of Subjects

Identifiers (name, medical record number) will be collected but will be replaced by study numbers in the analytical file. Scan/report dates will also be collected as part of this study, in order to identify different scans from the same patient. The key linking these numbers will be retained in a restricted database by the investigator. All study personnel have completed training in methods for maintaining the confidentiality of health information. Electronic records will be stored on password protected institution computers behind the institution firewall. Only the PI and research staff involved in the study will have access to this data. Complete confidentiality will be maintained during this retrospective evaluation, manuscript preparation, and submission.

Study sponsors and/or supporters receive limited amounts of PHI. They may also view additional PHI in study records during the monitoring

process. MD Anderson's contracts require sponsors/supporters to protect this information and limit how they may use it

## 17.0 Compensation for Research-Related Injury

17.1 The research involves only minimal risk to subjects. The patients will not be compensated for their participation.

## 18.0 Economic Burden to Subjects

18.1 The patients are not expected to encounter out of pocket costs. The cost of the imaging and IV contrast for the study is expected to be covered by a combination of insurance, GEIK grant, and an internal DICRC grant. The costs of biospecimen collection, questionnaire administration, and data storage will be covered by the Little Green Book Foundation.

## **19.0 Resources Available**

19.1 A full-field digital mammography system capable of providing lowand high-energy exposures to the breast under the same compression, as well as producing subtracted contrast images, such as Senographe Pristina (GE Healthcare, Buc, FR)

19.2 A CEM- guided biopsy device (GE Healthcare, Buc, FR) is planned to be installed in November 2020

*19.3 %FTE is requested for a dedicated clinical mammography technologist and a clinical study coordinator* 

19.4 Approximately 5-8 patients per day are seen in the multidisciplinary clinic for staging of BC diagnosed at OSF. This results in a minimum of 1,305 potentially eligible patients. Recruiting 6% of the eligible pool, or 2 patients per week will allow completion of recruitment within 12 months.

# 20.0 Multi-Site Research\*

N/A

